### 7.6.5.3. Statistical Analyses / Methods

Summary statistics for BFI total score at each week of treatment will be presented, including change from baseline values. Assessment windows for each week are defined in Section 16.3.1.

Endpoint

 
Change from baseline in BFI total score at Week 32.
 

Model Specification

 
Wilcoxon Rank Sum test stratified by median baseline fatigue (baseline fatigue<math>\leq</math>median and baseline fatigue<math>></math>median), baseline OCS dose (0-<math>\leq</math>20mg/day and <math>></math>20mg/day prednisone or equivalent) and region.
 

Model Results Presentation

 
Number analysed in each treatment group.
 
Median change from baseline at Week 32 in each treatment group.
 
p-value for difference between treatments from Wilcoxon Rank Sum test.
 

Subgroup Analyses

 
No subgroup analyses will be performed on this endpoint.
 

Sensitivity and Supportive Statistical Analyses

 
For the change from baseline BFI total score, a repeated measures analysis including assessments at Week 4, 8, 12, 16, 20, 24, 28 and 32. In this analysis missing data will be assumed to be missing at random and will not be imputed with the largest i.e. worst value. A mixed effects model will be fitted with the following specification: 
 
Time point, treatment and region included as fixed categorical effects.
 
Baseline BFI total score and baseline OCS included as continuous fixed covariates.
 
Interaction terms for baseline-by-timepoint and treatment-by-time point interaction.
 
The Kenward and Roger method (DDFM = KR) for approximating the denominator degrees of freedom to correct for bias in the estimated variance-covariance matrix.
 
REPEATED statement with TYPE=UN to specify an unstructured covariance structure for the R matrix.
 
The OBSMARGIN option on the LSMEANS statement in order to compute the adjusted geometric means with weights proportional to the input data set.
 
 
 

## 7.6.6. Clinician- and Subject-Rated Overall Response to Therapy Score (RTS) at Week 32

### 7.6.6.1. Endpoint / Variables

- Clinician-rated overall response to therapy (significantly improved [1], moderately improved [2], mildly improved [3], no change [4], mildly worse [5], moderately worse [6] and significantly worse [7]) at Week 32.
- Subject-rated overall response to therapy (significantly improved [1], moderately improved [2], mildly improved [3], no change [4], mildly worse [5], moderately worse [6] and significantly worse [7]) at Week 32.

### 7.6.6.2. Strategy for Intercurrent (Post-Randomization) Events

The treatment effect to be estimated (estimand) will be the ‘treatment policy’ effect of initial randomised treatment. A treatment policy strategy will be used for the intercurrent events of a) discontinuation of study medication and b) receipt of alternative HES medications. Subjects with missing response at Week 32 will be included in the analysis with the largest (i.e. worst) value observed for any subject.

### 7.6.6.3. Statistical Analyses / Methods

Summary statistics for clinician- and subject- rated overall response to therapy at each visit will be presented.

Endpoint

 
• Clinician-rated overall response to therapy at Week 32.
 
• Subject-rated overall response to therapy at Week 32
 

Model Specification

 
• Wilcoxon Rank Sum test stratified by baseline OCS dose (0-≤20mg/day and >20mg/day prednisone or equivalent) and region.
 
• Supplemented by an ordinal logistic regression (proportional odds) analysis adjusting for covariates of baseline OCS dose (continuous scale), region and treatment.
 

Model Results Presentation

 
• Number analysed in each treatment group.
 
• Median change from baseline at Week 32 in each treatment group.
 
• p-value for difference between treatments from Wilcoxon Rank Sum test.
 
• Odds ratio and 95% CI from ordinal logistic regression model.
 
• p-value from ordinal logistic regression model.
 

Subgroup Analyses

 
• No subgroup analyses will be performed on this endpoint.
 

Sensitivity and Supportive Statistical Analyses

 
• Clinician- and subject-rated overall response to therapy will also be analysed at Week 4, 8, 12, 16, 20, 24 and 28 in the same way as the Week 32 analysis.
 

### 7.6.7. Change from Baseline in Subject-Rated Symptom Severity (SSR) at Week 32

#### 7.6.7.1. Endpoint / Variables

At each visit, subjects are asked to rate their symptoms of HES now as none (0), mild (1), moderate (2), severe (3) or very severe (4). The change from baseline at Week 32 will be calculated from the Week 32 assessment and the Week 0 assessment and expressed in terms of number of categories of improvement or worsening of symptoms i.e. 4 point improvement (-4), 3 point improvement (-3), 2 point improvement (-2), 1 point improvement (-1), no change (0), 1 point worsening (1), 2 point worsening (2), 3 point worsening (3) or 4 point worsening (4).

#### 7.6.7.2. Strategy for Intercurrent (Post-Randomization) Events

The treatment effect to be estimated (estimand) will be the ‘treatment policy’ effect of initial randomised treatment. A treatment policy strategy will be used for the intercurrent events of a) discontinuation of study medication and b) receipt of alternative HES medications. Subjects with missing SSR score at Week 32 will be included in the analysis with the largest (i.e. worst) value observed for any subject.

#### 7.6.7.3. Statistical Analyses / Methods

Summary statistics for the SSR score at each visit will be presented, as well as the change from baseline.

Endpoint

 
Change from baseline in subject-rated symptom severity (SSR) at Week 32.
 

Model Specification

 
Wilcoxon Rank Sum test stratified by baseline OCS dose (0-≤20mg/day and >20mg/day prednisone or equivalent) and region.
 
Supplemented by an ordinal logistic regression (proportional odds) analysis adjusting for covariates of baseline OCS dose (continuous scale), region and treatment.
 

Model Results Presentation

 
Number analysed in each treatment group.
 
Median change from baseline at Week 32 in each treatment group.
 
p-value for difference between treatments from Wilcoxon Rank Sum test.
 
Odds ratio and 95% CI from ordinal logistic regression model.
 
p-value from ordinal logistic regression model.
 

Subgroup Analyses

 
No subgroup analyses will be performed on this endpoint.
 

Sensitivity and Supportive Statistical Analyses

 
No sensitivity analyses will be performed.
 

## 7.6.8. Change from Baseline in Modified Memorial Symptom Assessment Scale-Short Form (MSAS-SF) responses at Week 32

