## 5.4. Examination of Covariates, Other Strata and Subgroups

### 5.4.1. Covariates and Other Strata

- Region and baseline OCS dose, expressed as prednisone equivalent dose, will be covariates in all statistical analysis. These covariates will be included as stratification variables for the Cochran-Mantel-Haenszel test and Wilcoxon Rank Sum test according to the table below. For parametric analysis models, region will be included as a fixed categorical effect and baseline OCS dose will be included as a fixed continuous effect.

Category	Covariates and / or Subgroups
Region	See Section 5.3. 
 
USA
 
Argentina, Mexico and Brazil
 
Rest of World
 

Baseline oral prednisone equivalent dose 	See Section 5.4.1.1 
 
0-≤20mg prednisone or equivalent
 
>20mg prednisone or equivalent
 

For parametric analysis models, baseline OCS dose will be included as a fixed continuous effect.

- If the percentage of subjects is small within a region, then the region categories may be refined prior to unblinding the trial.
- For analyses where a baseline value of the analysis variable is available this will also be included in the statistical analysis. These covariates will be included as stratification variables for the Cochran-Mantel-Haenszel test and Wilcoxon Rank Sum test, and as continuous fixed effects for all parametric analysis models.

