### **7.5.4. Statistical Analyses / Methods**

Details of the planned displays are provided in [Appendix 10](#): List of Data Displays and will be based on GSK data standards and statistical principles.

Summary statistics for BFI item 3 at each week of treatment will be presented, including change from baseline values. Assessment windows for each week are defined in [Section 16.3.1](#).

The clinical relevance of changes in BFI item 3 at Week 32 will be assessed using a cumulative distribution plot showing the percentage of subjects in each treatment group with a reduction in BFI item 3 greater than equal to each value in the observed range; this will allow assessment of the treatment difference against a range of clinically important differences.

Endpoint

 
Change from baseline in fatigue severity (BFI item 3) at Week 32.
 

Model Specification

 
Wilcoxon Rank Sum test stratified by baseline fatigue severity (“severe” defined as BFI item 3 <math>\geq 7</math>, and “not severe” defined as BFI item 3 <math>< 7</math>), baseline OCS dose (<math>0 \leq 20</math>mg/day and <math>> 20</math>mg/day prednisone or equivalent) and region. This will be implemented using the FREQ procedure with the SCORES = MODRIDIT option.
 

Model Checking & Diagnostics

 
Not applicable.
 

Model Results Presentation

 
Number analysed in each treatment group.
 
Median change from baseline BFI item 3 at Week 32 in each treatment group.
 
p-value for difference between treatments from Wilcoxon Rank Sum test.
 

Subgroup Analyses

 
No subgroup analyses will be performed on this endpoint.
 

Sensitivity and Supportive Statistical Analyses

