### 7.6.4.3. Statistical Analyses / Methods

Summary statistics for the most bothersome symptom score and the symptom score for each symptom domain at each week of treatment will be presented, including change from baseline values. Assessment windows for each week are defined in Section 16.3.1.

Endpoint

 
Change from baseline in most bothersome HES symptom severity score (HES-DS) at Week 32.
 
Change from baseline in HES symptom severity score (HES-DS) for each symptom at Week 32.
 

Model Specification

 
Wilcoxon Rank Sum test stratified by median baseline symptom severity (baseline symptom severity <math>\leq</math> median and baseline symptom severity <math>></math> median), baseline OCS dose (<math>0 \leq 20</math> mg/day and <math>>20</math> mg/day prednisone or equivalent) and region.
 

Model Results Presentation

 
Number analysed in each treatment group.
 
Median change from baseline at Week 32 in each treatment group.
 
p-value for difference between treatments from Wilcoxon Rank Sum test.
 

Subgroup Analyses

 
No subgroup analyses will be performed on this endpoint.
 

Sensitivity and Supportive Statistical Analyses

 
Repeated measures analysis including assessments at Week 4, 8, 12, 16, 20, 24, 28 and 32. In this analysis missing data will be assumed to be missing at random and will not be imputed with the largest i.e. worst value. A mixed effects model will be fitted with the following specification: 
 
Time point, treatment and region included as fixed categorical effects.
 
Baseline symptom severity and baseline OCS included as continuous fixed covariates.
 
Interaction terms for baseline-by-timepoint and treatment-by-time point interaction.
 
The Kenward and Roger method (DDFM = KR) for approximating the denominator degrees of freedom to correct for bias in the estimated variance-covariance matrix.
 
REPEATED statement with TYPE=UN to specify an unstructured covariance structure for the R matrix.
 
The OBSMARGIN option on the LSMEANS statement in order to compute the adjusted geometric means with weights proportional to the input data set.
 
 
 

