#### 10.2.5.1. Statistical Methodology Specification

Endpoint

 
• Ratio to baseline total IL-5 at Week 32
 

Model Specification

 
• Wilcoxon Rank Sum test stratified by baseline OCS dose (<math>0 \leq 20</math>mg/day and <math>>20</math>mg/day prednisone or equivalent) and region.
 

Model Results Presentation

 
• Number analysed in each treatment group.
 
• Median change from baseline at Week 32 in each treatment group.
 
• p-value for difference between treatments from Wilcoxon Rank Sum test.
 

Subgroup Analyses

 
• No subgroup analyses will be performed on this endpoint.
 

Sensitivity and Supportive Statistical Analyses

 
• No sensitivity analyses will be performed.
 

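### The analysis of change in subject-rated symptom severity omits baseline severity, against the SAP's own covariate rule, which costs power and leaves baseline imbalance unadjusted

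*SAP*

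**What the plan says.** - **SSR endpoint (SAP 7.6.7.1).** Symptoms are scored in five categories, from 0 (none) to 4 (very severe). "The change from baseline at Week 32 will be calculated from the Week 32 assessment and the Week 0 assessment", so every subject with a change score has a baseline value.
- **SSR analysis (SAP 7.6.7.3).** The Wilcoxon test is stratified by baseline OCS dose (two levels) and region (three levels). It is followed by: "Supplemented by an ordinal logistic regression (proportional odds) analysis adjusting for covariates of baseline OCS dose (continuous scale), region and treatment". Baseline SSR appears in neither, and the section plans no sensitivity analysis.
- **General rule (SAP 5.4.1).** "For analyses where a baseline value of the analysis variable is available this will also be included in the statistical analysis". The section then says how: as a stratification variable in the Cochran-Mantel-Haenszel and Wilcoxon tests "and as continuous fixed effects for all parametric analysis models".
- **Other patient-reported change scores.** All carry a baseline stratum. BFI item 3 (7.5.4): "Wilcoxon Rank Sum test stratified by baseline fatigue severity". HES-DS (7.6.4.3): "Wilcoxon Rank Sum test stratified by median baseline symptom severity". BFI total (7.6.5.3), MSAS-SF (7.6.8.3) and PROMIS (7.6.9.3) also split at the baseline median.
- **Total IL-5 (SAP 10.2.5.1).** The endpoint is a ratio to baseline, but the test is a "Wilcoxon Rank Sum test stratified by baseline OCS dose" and region only.

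SAP 2.4, which lists changes from the protocol, gives no reason to exempt SSR or IL-5. The February 2019 and June 2019 versions of the SAP specify the same SSR terms.

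**The concern.** A programmer working from 5.4.1 and one working from 7.6.7.3 would report different p-values and odds ratios for the same endpoint.

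The omission also matters statistically. On a 0 to 4 scale the possible change depends directly on where the subject starts: a subject at 0 cannot improve and a subject at 4 cannot worsen. A raw change score therefore carries baseline variation into the treatment comparison. Randomisation is stratified by region only, so nothing in the design balances baseline SSR, and no other planned SSR analysis adjusts for it. Any chance difference between arms at Week 0 passes into the estimated odds ratio.

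The SSR specification reads like the one for the overall response to therapy score (7.6.6.3). That score has no baseline value, so it is no precedent for leaving baseline out here.

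**Working it through.** **Plan's own figure.** The documents give no power for SSR. The only stated power is for the primary endpoint (protocol 9.2.1): 60% v 22%, 40 per arm, two-sided 5%, 90% power. Fisher's exact test gives 91.9% and the continuity-corrected normal approximation 91.5%, so the sample size and alpha used below are those of the plan.

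**Analytic check.** With equal variances and baseline-to-Week 32 correlation ρ, raw change has variance proportional to 2(1 − ρ) and the baseline-adjusted outcome 1 − ρ². The ratio is (1 − ρ²) / [2(1 − ρ)] = (1 + ρ)/2, which is 0.65, 0.75 and 0.85 at ρ = 0.3, 0.5 and 0.7. Adjustment always helps, and helps less as ρ rises.

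**Simulation inputs.** From the documents: 40 per arm, two OCS strata, three regions, allocation balanced within region, a five-category scale. Assumed: baseline split 8/27/40/20/5% across scores 0 to 4, latent treatment shift 0.6 SD, ρ of 0.3 to 0.7, regions 25/25/50%, 20% of subjects above 20 mg OCS, no missing data. In the ordinal model OCS dose was entered as the two-level split. The stratified Wilcoxon (van Elteren, modified ridit scores) used 8,000 runs, with Monte Carlo error about 0.6 point. The proportional-odds model used 600 runs, with error about 2 points.

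| ρ | Wilcoxon, no baseline | Wilcoxon, median split | Gain | Ordinal, no baseline | Ordinal, with baseline | Gain |
|---|---|---|---|---|---|---|
| 0.3 | 50.7% | 58.0% | 7.3 | 56.5% | 75.5% | 19.0 |
| 0.5 | 61.8% | 66.4% | 4.6 | 69.0% | 80.8% | 11.8 |
| 0.7 | 79.0% | 80.8% | 1.8 | 82.0% | 90.3% | 8.3 |

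With no treatment effect the ordinal model rejected in 5.3 to 7.0% of runs (error about 0.9 point). At ρ = 0.3 the rate was 5.3% without baseline and 7.0% with it, so a small part of that gain may be slight anti-conservatism. Two further sets of runs at ρ = 0.3 and 0.5 agreed: Wilcoxon gains of 4 to 7 points and ordinal gains of 15 to 25 points.

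**Imbalance.** Under the assumed split:

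- Mean score = 0.27 + 0.80 + 0.60 + 0.20 = 1.87.
- Mean square = 0.27 + 1.60 + 1.80 + 0.80 = 4.47.
- Variance = 4.47 − 1.87² = 0.973, so SD = 0.986.
- SD of the between-arm difference in means = 0.986 × √(2/40) = 0.22 category.

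A gap above 0.22 arose in about 32% of simulated trials. With no treatment effect, each one-category gap moved the difference in mean change by −0.74, −0.54 and −0.36 at the three correlations. A gap of 0.22 therefore moves it by about −0.16, −0.12 and −0.08.

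Two-sided false-positive rate of the Wilcoxon given a gap above 0.22:

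| ρ | No baseline | Median split | All five categories |
|---|---|---|---|
| 0.3 | 10.7% | 7.0% | 5.8% |
| 0.5 | 8.9% | 6.1% | 4.5% |
| 0.7 | 8.3% | 5.6% | 4.9% |

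Averaged over all randomisations, the unadjusted Wilcoxon rejects in 4.7 to 5.5% of null trials.

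**The case against.** The strongest reply is that little depends on this. SSR is exploratory and outside the five-endpoint hierarchy in SAP 5.5, and the fatigue endpoint inside the hierarchy already has a baseline stratum. Section 5.4.1 could be read as adding baseline by default, which would make this a drafting gap and not a choice. That limits the importance, but 7.6.7.3 lists its terms in full without baseline, so a reader cannot tell which section governs.

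Second, the Wilcoxon is the main SSR test, and its gain is modest and rests on assumed inputs. This stands. Giving missing subjects the worst observed change, in the spirit of SAP 7.6.7.2, shrinks the gain further. In a separate set of 6,000 runs, with none, 10% and 20% missing, it was 6.7, 5.1 and 2.9 points at ρ = 0.3, and 4.3, 3.7 and 2.6 at ρ = 0.5. At ρ = 0.7 it was about 1 point or less throughout.

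Third, the imbalance problem is conditional on the gap that occurs; overall type I error is not inflated. This is correct. A median split is also only a partial cure. Under the assumed distribution, scores 0, 1 and 2 (8 + 27 + 40 = 75% of subjects) fall in one stratum, so the floor is not isolated.

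Fourth, twelve strata in 80 subjects average 80/12 = 6.7 each, and about 5 subjects per trial fell in single-arm strata and contributed nothing. That cost is real, but the SAP already accepts it for the other patient-reported scores.

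The IL-5 point has no power calculation behind it and stands only as the same departure from 5.4.1.

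**Conclusion.** The concern holds. SAP 7.6.7.3 leaves out a term that SAP 5.4.1 requires, the value is collected, the comparable endpoints include it, and no exemption is stated. Total IL-5 in 10.2.5.1 has the same omission.

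Under the stated assumptions, power falls by about 2 to 7 points in the main test and 8 to 19 points in the supplementary model. The larger losses occur at lower correlation, and worst-value imputation shrinks the Wilcoxon loss. Overall type I error is sound; the unadjusted comparison is unreliable when the arms happen to differ at Week 0. The contradiction does not depend on any simulated figure. No confirmatory conclusion is at risk, so this should be corrected but does not threaten the trial.

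**What to change.** - In SAP 7.6.7.3, add the baseline SSR score as a covariate in the proportional-odds model. This is where most of the power is recovered.
- In the same section, add a baseline SSR split (at or below the median, above the median) to the Wilcoxon strata, as for the other patient-reported change scores.
- In SAP 10.2.5.1, add a baseline split to the total IL-5 Wilcoxon test.
- If either endpoint is meant to be exempt, say so with the reason and amend 5.4.1 to match.

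The cost is SAP wording and one extra term per analysis, using data already collected. The SSR Wilcoxon goes from 6 to 12 strata. Settle this before unblinding, so that the choice between two written specifications cannot be influenced by the results.

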### 7.6.8.1. Endpoint / Variables

The MSAS-SF questionnaire records the distress or bother in the last week caused by each of 28 symptoms on 5-point scale (not at all, a little bit, somewhat, quite a bit, very much) as well as how often during the last week a further 4 symptoms occurred on a 4-point scale (occurs rarely, occasionally, frequently, almost constantly). Conversion of each of the categorical responses to a numeric score will be performed as described in the table below.

Question Type	Categorical Response	Numeric Score
Distress or bother (28 symptoms)	Symptom is absent	0
	Symptom present but causes no distress or bother (i.e. level of distress or bother categorised as "not at all")	0.8
	Symptom present and causes a little bit of distress or bother	1.6
	Symptom present and causes somewhat of distress or bother	2.4
	Symptom present and causes quite a bit of distress or bother	3.2
	Symptom present and causes very much distress or bother	4.0
How often (4 symptoms)	Symptom is absent	0
	Symptom present and occurs rarely	1
	Symptom present and occurs occasionally	2
	Symptom present and occurs frequently	3
	Symptom present and occurs almost constantly	4

Using the numeric conversion above, the following endpoints will be derived:

- Total MSAS-SF score for each visit will be calculated as the mean of the 32 scores recorded for that visit.
- MSAS-SF global distress index (GDI) for each visit will be calculated as the mean of the scores for 10 symptoms (feeling sad, worrying, feeling irritable and feeling nervous, lack of energy, pain, lack of appetite, feeling drowsy, constipation, dry mouth).
- MSAS-SF physical symptom subscale score for each visit will be calculated as the mean of the scores for 12 physical symptoms (lack of energy, pain, lack of appetite, feeling drowsy, constipation, dry mouth, nausea, vomiting, change in taste, weight loss, feeling bloated, and dizziness).

- MSAS-SF psychological symptom subscale score for each visit will be calculated as the mean of the scores for 6 psychologic symptoms (worrying, feeling sad, feeling nervous, difficulty sleeping, feeling irritable, and difficulty concentrating).

For each score the change from baseline at Week 32 will be calculated from the assessment at Week 0 and Week 32.

#### 7.6.8.2. Strategy for Intercurrent (Post-Randomization) Events

The treatment effect to be estimated (estimand) will be the ‘treatment policy’ effect of initial randomised treatment. A treatment policy strategy will be used for the intercurrent events of a) discontinuation of study medication and b) receipt of alternative HES medications. Subjects with missing change from baseline MSAS-SF score at Week 32 will be included in the analysis with the largest (i.e. worst) value observed for any subject.

#### 7.6.8.3. Statistical Analyses / Methods

Summary statistics for MSAS-SF scores at each visit will be presented, including change from baseline values.

Endpoint

 
• Change from baseline in Total Modified Memorial Symptom Assessment Scale-Short Form (MSAS-SF) score at Week 32.
 
• Change from baseline in Modified Memorial Symptom Assessment Scale-Short Form (MSAS-SF) global distress index at Week 32.
 
• Change from baseline in Modified Memorial Symptom Assessment Scale-Short Form (MSAS-SF) physical symptom subscale score at Week 32.
 
• Change from baseline in Modified Memorial Symptom Assessment Scale-Short Form (MSAS-SF) psychological symptom subscale score at Week 32.
 

Model Specification

 
• Wilcoxon Rank Sum test stratified by median baseline score (baseline score ≤ median and baseline score > median), baseline OCS dose (0 ≤ 20mg/day and >20mg/day prednisone or equivalent) and region.
 

Model Results Presentation

 
• Number analysed in each treatment group.
 
• Median change from baseline at Week 32 in each treatment group.
 
• p-value for difference between treatments from Wilcoxon Rank Sum test.
 

Subgroup Analyses

 
• No subgroup analyses will be performed on this endpoint.
 

Sensitivity and Supportive Statistical Analyses

 
• A repeated measures analysis including assessments at Week 4, 8, 16, 24 and 32. In this analysis missing data will be assumed to be missing at random and will not be imputed with the largest i.e. worst value. A mixed effects model will be fitted with the following specification:
 

- Time point, treatment and region included as fixed categorical effects.
- Baseline score and baseline OCS dose included as continuous fixed covariates.
- Interaction terms for baseline-by-timepoint and treatment-by-time point interaction.
- The Kenward and Roger method (DDFM = KR) for approximating the denominator degrees of freedom to correct for bias in the estimated variance-covariance matrix.
- REPEATED statement with TYPE=UN to specify an unstructured covariance structure for the R matrix.
- The OBSMARGIN option on the LSMEANS statement in order to compute the adjusted geometric means with weights proportional to the input data set.

**7.6.9. Change from Baseline in Physical Function and Sleep (Patient Reported Outcome Measurement Information System [PROMIS]) at Week 32**

